2.3 Benefit/Risk Assessment

At the time of study initiation, bintrafusp alfa demonstrated promising clinical efficacy in a cohort of participants with second-line (2L)+ cervical cancer in the Phase I study EMR200647-001, with a confirmed ORR of 24.0% and total clinical response rate of 28.0% (95% CI: 12.1, 49.4). The median DOR had not been reached by data cutoff - 5 of 6 responses were ongoing, with 1 ongoing response already lasting for > 2 years. These results demonstrate encouraging clinical efficacy of bintrafusp alfa in cervical cancer with favorable response rate and durability compared to historical benchmarks.

Platinum-containing chemotherapy regimen with or without bevacizumab is the standard first-line therapy for patients with metastatic cervical cancer. For patients with advanced unresectable and/or metastatic cervical cancer with disease progression during or after platinum-based chemotherapy there is no established consensus for second-line treatment options due to low response rates, typically short-lived and variable toxicities (Bookman 2000; Muderspach 2001; Schilder 2005; Alberts 2012). Based upon the poor clinical prognosis new treatment options for this patient population are needed, and these patients are included in the eligibility for this study (further rationale included in Section 4.2).

The identified and potential risks with bintrafusp alfa monotherapy were overall manageable and no new safety signals emerged in the Phase I studies (EMR200647-001, MS200647-0008) compared with therapies targeting PD-L1 or TGF- β . The following have been identified as important identified risks for M7824: Immune-related adverse events (immune-related pneumonitis, immune-related hepatitis, immune-related colitis, immune-related nephritis and renal dysfunction, immune-related endocrinopathies [thyroid disorders, adrenal insufficiency, Type 1 Diabetes mellitus, pituitary disorders], immune-related rash and other immune-related adverse events (irAEs) [myositis, myocarditis, encephalitis]), TGF- β inhibition mediated skin reactions, anemia and bleeding adverse events. The overall incidence and severity for irAEs is found to be consistent across bintrafusp alfa studies and similar to the known safety profile of approved anti-PD-L1 agents (Brahmer 2018).

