4.0 Endocrine Toxicity	
Laboratory evaluation in suspected T1DM should include testing for ketosis in urine and an assessment of the anion gap on a metabolic panel. Anti–glutamic acid decarboxylase, anti–islet cell, or anti–insulin antibodies are highly specific for autoimmune diabetes. Insulin and C-peptide levels can also assist in the diagnosis.	
Grading	Management
G1: Asymptomatic or mild symptoms; fasting glucose value > ULN (160 mg/dL); fasting glucose value > ULN (8.9 mmol/L); no evidence of ketosis or laboratory evidence of T1DM	Can continue ICPI with close clinical follow-up and laboratory evaluation May initiate oral therapy for those with new-onset T2DM Screen for T1DM if appropriate, for example, acute onset with prior normal values or clinical concern for ketosis
G2: Moderate symptoms, able to perform ADL, fasting glucose value > 160-250 mg/dL; fasting glucose value > 8.9-13.9 mmol/L, ketosis or evidence of T1DM at any glucose level	May hold ICPI until glucose control is obtained Titrate oral therapy or add insulin for worsening control in T2DM Should administer insulin for T1DM (or as default therapy if there is confusion about type) Urgent endocrine consultation for any patient with T1DM; in the absence of endocrinology, internal medicine may suffice Consider admission for T1DM if early outpatient evaluation is not available or signs of ketoacidosis are present
G3-4: Severe symptoms, medically significant or life-threatening consequences, unable to perform ADL G3: > 250-500 mg/dL (> 13.9-27.8 mmol/L) G4: > 500 mg/dL (> 27.8 mmol/L)	Hold ICPI until glucose control is obtained on therapy with reduction of toxicity to G1 or less Urgent endocrine consultation for all patients Initiate insulin therapy for all patients Admit for inpatient management: Concerns for developing DKA, Symptomatic patients regardless of diabetes type, New-onset T1DM unable to see endocrinology

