15.3 Clinical Laboratory Evaluation

Baseline and on-treatment laboratory values (including corresponding normal ranges), converted in standard unit, will be used for boxplots and shift tables.

Laboratory results will be classified according to the NCI-CTCAE criteria version 5.0 and as specified in [Appendix 2: Definition of NCI-CTCAE grading](#). Additional laboratory results that are not part of NCI-CTCAE will be categorized as follows: below normal limits, within normal limits, and above normal limits (according to the original laboratory normal ranges).

The following figures will be provided for hematology and biochemistry parameters:

- Boxplots of the laboratory values by timepoint
- Boxplots of the change from baseline by timepoint

Boxplots will display scheduled visits per protocol. In case two values are related to the same visit, the first result will be used.

Boxplots for laboratory parameters where toxicity grades are defined based on the ratio of the parameter values and the upper limit of normal (ULN) will not be displayed using the unit of measurement but instead using the ratio of the measured value over ULN. This comprises alkaline phosphatase (ALP), alanine aminotransferase (ALT), aspartate aminotransferase (AST), Activated Partial Thromboplastin Time (aPTT), bilirubin, and creatinine.

Laboratory parameters with NCI-CTC grades available

Laboratory parameters with NCI-CTC grades available will be analyzed with their respective NCI-CTC name and direction of abnormality. For parameters which are graded with both low and high values as potassium (hypokalemia/hyperkalemia), the toxicities will be summarized separately. Low direction toxicity (e.g. hypokalemia) grades at baseline and post-baseline will be set to 0 when the variables are derived for summarizing high direction toxicity (e.g. hyperkalemia), and vice versa.

The following summaries will be displayed:

- Number and percentage of participants by worst on-treatment grade (≥ 1 , ≥ 3 , ≥ 4)
- Shift in toxicity grading from baseline to highest on-treatment toxicity grade

The definitions of the NCI-CTCAE toxicity grading version 5.0 for each parameter are provided in [Appendix 2: Definition of NCI-CTCAE grading](#) of this IAP.

Table 10 NCI-CTC Gradable parameters

Parameter	Parameter code	Name in NCI-CTC	Direction of abnormality
Biochemistry			
Alanine Aminotransferase ^c	ALT	Alanine aminotransferase increased	High
Albumin	ALB	Hypoalbuminemia	Low

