Alkaline Phosphatase ^c	ALP	Alkaline phosphatase increased	High
Amylase	AMYLASE	Serum amylase increased	High
Aspartate Aminotransferase ^c	AST	Aspartate aminotransferase increased	High
Bilirubin total ^c	BILI	Blood bilirubin increased	High
Corrected Calcium ^a	CA	Hypercalcemia/Hypocalcemia ^a	High/Low
Creatinine ^c	CREAT	Creatinine increased	High
Glucose	GLUC	Hypoglycemia	Low
Lipase	LIPASET	Lipase increased	High
Potassium	K	Hyperkalemia/Hypokalemia	High/Low
Sodium	SODIUM	Hypernatremia/Hyponatremia	High/Low

Parameter	Parameter code	Name in NCI-CTC	Direction of abnormality
Hematology			
Absolute eosinophils ^c	EOS	Eosinophilia	High
Absolute lymphocyte	LYM	Lymphocyte count decreased/Lymphocyte count increased	High/Low
Absolute neutrophils	NEUT	Neutrophil count decreased	Low
Hemoglobin	HGB	Anemia/Hemoglobin increased	Low/High
Leukocytes (WBC)	WBC	Leukocytosis/White blood cell decreased	High/Low
Platelets count	PLAT	Platelet count decreased	Low
Coagulation			
Activated Partial Thromboplastin Time ^b	APTT	Activated partial thromboplastin time prolonged	High
Prothrombin International Normalized Ratio ^b	INR	INR increased	High

^a based on corrected calcium (see [Appendix 2: Definition of NCI-CTCAE grading](#)).

^b reported on the "Coagulation" eCRF page.

^c baseline will be presented as Normal/Abnormal. In high direction low values will be accounted as normal and for low direction high values will be accounted as normal. For calcium, CTCAE grading is based on corrected calcium. Corrected calcium is calculated from albumin and calcium as follows based on the International System of Units (SI):

- Corrected calcium (mg/dL) = Calcium (mg/dL) – 0.8 [Albumin (g/dL)-4], or
- Corrected calcium (mmol/L) = measured total calcium (mmol/L) + 0.02 (40 – serum albumin [g/L])

Laboratory parameters with NCI-CTC grades not available

Table 11 Non-NCI-CTC Gradable Parameters

Parameter (LBTEST)	Parameter code
Biochemistry	
Bilirubin direct	BILDIR
Bilirubin Indirect	BILIND
Chloride	CL
C-Reactive Protein	CRP
Total Protein	PROT
Urea	UREA
Urea Nitrogen	BUN
Hematology	
Absolute Basophils	BASO
Absolute Eosinophils	EOS
Absolute Monocytes	MONO

Parameter (LBTEST)	Parameter code
Absolute Reticulocytes	RETI
Basophils/Leukocytes	BASOLE
Eosinophils/Leukocytes	EOSLE
Erythrocytes (RBC)	RBC
Hematocrit	HCT
Lymphocytes/Leukocytes	LYMLE
Mean Corpuscular Hemoglobin	MCH
Mean Corpuscular HGB Concentration	MCHC
Mean Corpuscular Volume	MCV
Monocytes/Leukocytes	MONOLE
Neutrophils/Leukocytes	NEUTLE

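### The laboratory tables summarize glucose only in the low direction, so a rise in glucose is counted in no worst-grade, category or shift table, although type 1 diabetes is a named risk of the drug

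*SAP*

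**What the plan says.** SAP section 15.3 divides laboratory parameters into two groups.

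- **Gradable parameters (Table 10).** The rule is that "Laboratory parameters with NCI-CTC grades available will be analyzed with their respective NCI-CTC name and direction of abnormality". Two tabular summaries follow: counts by worst on-treatment grade, and "Shift in toxicity grading from baseline to highest on-treatment toxicity grade". The glucose row reads "Glucose GLUC Hypoglycemia Low". A parameter analysed both ways looks different, for example "Potassium K Hyperkalemia/Hypokalemia High/Low".
- **Non-gradable parameters (Table 11).** These get counts by lowest on-treatment value, counts by highest on-treatment value, and a shift from baseline, each classified as low, normal or high. Glucose is not listed.

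The SAP also has a rule for results without a grade: "Additional laboratory results that are not part of NCI-CTCAE will be categorized as follows: below normal limits, within normal limits, and above normal limits". Protocol section 9.4.2, Table 13, makes the same commitment.

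On the clinical side, Protocol section 2.3 includes among the important identified risks "immune-related endocrinopathies [thyroid disorders, adrenal insufficiency, Type 1 Diabetes mellitus, pituitary disorders". Protocol section 6.9.2 repeats this. The diabetes part of Protocol Appendix 5, Table A4, calls for monitoring for high glucose and gives numeric bands for its severe grades: "G3: > 250-500 mg/dL (> 13.9-27.8 mmol/L) G4: > 500 mg/dL (> 27.8 mmol/L". Glucose is in the biochemistry panel (Protocol Appendix 6), which the schedule of activities collects from screening through treatment.

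**The concern.** The direction of glucose change that would signal immune-related diabetes is up. The only direction the laboratory tables count is down. Glucose is measured repeatedly, and corticosteroids used to treat immune-related events can also raise it, so high values are plausible in this trial. A reader of the clinical study report who wants to know how many participants moved from normal to high glucose on treatment would find no table with the answer. At stake is the completeness of the laboratory safety summary for a named risk. No estimate or decision rule depends on it.

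**Working it through.** The plan gives no figure to reproduce, so the check traces a high glucose value through every laboratory output in SAP section 15.3.

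**Step 1: the graded tables.** Six Table 10 rows carry both directions: corrected calcium, potassium, sodium, lymphocytes, hemoglobin and leukocytes. Glucose carries only "Hypoglycemia" and Low. Since gradable parameters are analysed under their listed name and direction, the worst-grade counts and the grade shift for glucose cover low values only.

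**Step 2: the normal-range tables.** The three low/normal/high summaries are specified for non-gradable parameters. Going through Table 11 row by row, glucose does not appear, so none of the three is produced for it.

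**Step 3: the count.** Tables 10 and 11 feed 2 + 3 = 5 tabular summaries. High glucose enters 0 of the 5. The separate liver function tables do not involve glucose.

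**Step 4: where high glucose can still be seen.**
- *Boxplots* of values and of change from baseline, for biochemistry. These use scheduled visits only, and the first result where two belong to one visit. SAP sections 9 and 9.11, by contrast, let unscheduled results count toward worst on-treatment values and shift tables. An unscheduled glucose value taken because a participant was unwell could be missing from the boxplots, yet would be caught by a shift table if there were one. Boxplots also give no participant counts against the normal range.
- *The biochemistry listing*, which carries the normal range, a low/normal/high indicator and a flag for the highest and lowest on-treatment value. It holds the data but does not summarize them.
- *AE tables* (SAP section 15.1.1) and *immune-related AE tables* (SAP section 15.2.3.2), if the event is reported. Under Protocol Appendix 4, an abnormal laboratory finding is reported as an AE only if it comes with clinical signs and symptoms, leads to discontinuation, or is judged medically important. The immune-related flag also needs a listed term, an onset window, a qualifying treatment (insulin counts), and either no clear alternative cause or a supportive biopsy. A rise attributed to corticosteroids could fail the cause criterion.

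**Step 5: possible reasons for the low-only row.** The content of SAP Appendix 2, which holds the grading definitions, is not in the text available for this review, so the reason cannot be checked. There are two cases:
- If the grading scale has a usable high-glucose grade, Table 10 leaves out a direction.
- If it has no value-based high-glucose grade (an assumption), the SAP's own normal-range fallback should cover that direction, and the SAP does not apply it.

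The gap exists in both cases.

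**Step 6: precedent and current relevance.** Absolute eosinophils appear in Table 10 (high) and again in Table 11, so listing one parameter in both tables is already part of this SAP. SAP section 6.1, which restricts reporting to an abbreviated report, keeps clinical laboratory evaluations, so the point still applies.

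**The case against.** The strongest reply is that the named risk is handled where it belongs, in the AE analyses. Protocol section 8.2.4 has investigators record clinically relevant laboratory changes as AEs. In Table A4, severe diabetes calls for insulin, a hold of study drug and urgent specialist input, so such a case is unlikely to remain an unreported number. All treatment-emergent events are tabulated by term and by worst grade, and type 1 diabetes has its own subcategory in the immune-related tables. The stated safety endpoint is AEs, not laboratory shifts. With about 135 participants in one arm, a reader can also find extreme values in the listing.

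Most of this stands. Clinically important diabetes should be visible in the report. It does not cover isolated or moderate rises that never become AEs, and a listing does not replace a count.

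A reader might infer more than the documents support, in two ways.
- *That a very high glucose would be recoded to grade 0 and presented as a false safety result.* SAP section 15.3 does set the opposite direction to 0, but that rule is written for parameters graded both ways, and glucose is not one of them. A participant with high glucose has no hypoglycemia, so grade 0 hypoglycemia is a correct entry. The high direction is simply not summarized.
- *That a definite number of participants would be missed.* Neither document gives a rate of high glucose, and nothing shows that those participants would escape the AE tables.

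Counting participants by the full set of Table A4 bands is also open to challenge. The lower bands are defined on fasting glucose, the grades depend on symptoms and ketosis as well, and no fasting requirement appears in the schedule.

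**Conclusion.** The point holds in a limited form. Followed as written, SAP section 15.3 puts high glucose into none of its five grade, category or shift summaries. The values remain in the boxplots and the listing, and in the AE and immune-related AE tables when reported as events. The number of participants affected is unknown and cannot be estimated from the documents.

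The conclusion rests on Tables 10 and 11 fixing what is tabulated. It assumes that the unseen SAP Appendix 2 does not add a high-glucose summary that Table 10 leaves out. No efficacy conclusion, decision rule or stated safety endpoint changes. This is a cheap improvement to the safety summary for a named important risk.

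**What to change.** Add glucose to Table 11 alongside its Table 10 entry, as is done for eosinophils. Report the highest on-treatment value as low, normal or high, and the shift from baseline against the normal range. Unscheduled results should count toward the worst value, as SAP section 9 already provides.

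Optionally, add descriptive counts of participants with any on-treatment glucose above 250 and above 500 mg/dL. Label these as glucose values of unknown fasting status, and not as Table A4 or CTCAE grades.

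The cost is one extra row in existing table shells, with no new data collection, plus a small count table if the option is taken. The downside is that some high values may come from non-fasting samples, which a footnote should say.

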 - a. Adequate hematological function defined by absolute neutrophil count (ANC) $\geq 1.5 \times 10^9/L$, platelet count $\geq 100 \times 10^9/L$, and hemoglobin (Hgb) ≥ 9 g/dL.

- b. Adequate hepatic function defined by a total bilirubin level \leq the upper limit of normal (ULN), aspartate aminotransferase (AST) and alanine aminotransferase (ALT) levels $\leq 1.5 \times$ ULN. For participants with liver involvement in their tumor, AST $\leq 5.0 \times$ ULN, ALT $\leq 5.0 \times$ ULN, and bilirubin $\leq 3.0 \times$ ULN are acceptable.
 - c. Adequate renal function defined by creatinine $\leq 1.5 \times$ ULN or calculated creatinine clearance (CrCL) ≥ 30 mL/min for participant with creatinine $> 1.5 \times$ ULN (glomerular filtration rate can also be used).
 - Note: CrCL should be calculated per institutional standard. If no local guideline is available, CrCL should be calculated using the Cockcroft-Gault Method:
$$\text{CrCL} = ([140 - \text{age}] \times \text{weight [kg]} \times [0.85 \text{ for females only}]) / (72 \times \text{creatinine}).$$
 - d. Adequate coagulation function defined as international normalized ratio (INR) or prothrombin time (PT) $\leq 1.5 \times$ ULN unless the participant is receiving anticoagulant therapy and activated partial thromboplastin time (aPTT) $\leq 1.5 \times$ ULN unless the participant is receiving anticoagulant therapy.
8. Participants with known HIV infections are in general eligible if the following criteria are met ([FDA Guidance on Cancer Clinical Trial Eligibility, March 2019](#)):
- a. If clinically indicated patients must be stable on antiretroviral therapy (ART) for at least 4 weeks and agree to adhere to ART. If not clinically indicated, consult study Medical Monitor.
 - b. Participants with HIV infection should have no evidence of documented multi-drug resistance that would prevent effective ART.
 - c. Have an HIV viral load of < 400 copies/mL at Screening.
 - d. Have CD4+ T-cell (CD4+) counts ≥ 350 cells/ μ L.
 - e. For patients with a history of an AIDS-defining opportunistic infection within the last 12 months, patients may be eligible only after consultation and agreement with the study Medical Monitor.
 - f. If prophylactic antimicrobial drugs are indicated, patient may still be considered eligible upon agreement with the study Medical Monitor.

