- Isolated laboratory values out of normal range that do not have any clinical correlation. Discuss with Medical Monitor regarding work-up, management, and treatment continuation versus hold versus discontinuation for isolated Grade 4 laboratory abnormalities
- If alternative explanation is identified for Grade 4 non-tumor bleeding.

See [Appendix 5](#) for guidance on specific Grade 4 irAEs, as most require permanent treatment discontinuation.

Grade 3 treatment-related TEAE

1. Participants with any severe or Grade 3 treatment-related adverse reactions that recur should be permanently discontinued. Exceptions may be considered for the following after discussion with Medical Monitor:
 - Transient Grade 3 flu-like symptoms or fever that is controlled with medical management

- Transient Grade 3 fatigue, local reactions, headache, nausea, emesis that resolves to \leq Grade 1 or baseline
 - Tumor flare phenomenon defined as local pain, irritation, or rash localized at sites of known or suspected tumors
 - Any Grade \geq 3 drug-related amylase or lipase abnormality that is not associated with symptoms or clinical manifestations of pancreatitis
 - Grade 3 Hgb decrease (< 8.0 g/dL) that is clinically manageable with blood transfusions or erythroid growth factor use
 - Increases in ECOG PS \geq 3 that resolves to \leq 2 by Day 1 of the next infusion (i.e., infusions should not be given if the ECOG PS is \geq 3 on the day of treatment and should be delayed until ECOG PS \leq 2)
 - Keratoacanthoma (KA) and cutaneous squamous cell carcinoma (cSCC)
 - Grade 3 non-tumor bleeding requiring intervention or hospitalization if alternative explanation can be identified (such as concomitant use of antithrombotic agents, traumatic event, etc.).
2. See [Appendix 5](#) for guidance on specific Grade 3 irAEs as many require permanent treatment discontinuation, including pneumonitis and nephritis.
 - AST or ALT $>$ 5 times ULN or total bilirubin greater than 3 times ULN must be permanently discontinued, except for participants with liver metastases (for example) who begin treatment with Grade 2 AST or ALT. These participants should be discontinued if AST or ALT increases by \geq 50% relative to baseline and lasts for at least 1 week.
 3. Persistent Grade 3 adverse reactions (excluding endocrinopathies controlled with hormone replacement therapy) that do not recover to Grade 0 to 1 within 12 weeks after dose of treatment.

Grade 2 treatment-related TEAE

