Reticulocytes/Erythrocytes	RETIRBC
Coagulation	
Prothrombin Time*	PT

* reported on the "Coagulation" eCRF page.

Calcium will be listed but not summarized

For all non-gradable parameters, the following summaries will be displayed:

- Number and percentage of participants by lowest on-treatment value (classified as normal, high, low)
- Number and percentage of participants by highest on-treatment value (classified as normal, high, low)
- Shift from baseline to highest/lowest on-treatment value (classified as normal, high, low)

In case the indirect bilirubin is not provided in the database but, at the same time point, data are provided for both total bilirubin and direct bilirubin, the missing value will be estimated using the formula: indirect bilirubin = total serum bilirubin - direct bilirubin

Separate listings of hematology (including coagulation) and biochemistry will be created. Each listing will include: participant identifier, age, sex, race, first dose date, last dose date, laboratory parameter (units), visit, date, SI value, change from baseline value, lower limit of normal, ULN, indicator of normal range (low, normal, high), toxicity grade according to NCI-CTCAE (when applicable) and highest/lowest on treatment value flag. Baseline and post-baseline values after the on-treatment period will be flagged. These listings will be sorted by participant identifier, parameter and laboratory measurement date.

The laboratory shift tables may be repeated for China sub-population.

Liver function tests

ALT, AST and total bilirubin are used to assess possible drug induced liver toxicity. The ratios of test result over ULN will be calculated and classified for these three parameters during the on-treatment period.

The number and percentage of participants within each of the following liver function categories during on-treatment period will be described:

- ALT < 3×ULN, ALT ≥ 3×ULN, ALT ≥ 5×ULN, ALT ≥ 10×ULN, ALT ≥ 20×ULN
- AST < 3×ULN, AST ≥ 3×ULN, AST ≥ 5×ULN, AST ≥ 10×ULN, AST ≥ 20×ULN
- (ALT and AST) < 3×ULN, (ALT or AST) ≥ 3×ULN, (ALT or AST) ≥ 5×ULN, (ALT or AST) ≥ 10×ULN, (ALT or AST) ≥ 20×ULN
- Total Bilirubin (TBILI) < 2×ULN, TBILI ≥ 2×ULN
- Concurrent ALT ≥ 3×ULN and TBILI ≥ 2×ULN
- Concurrent AST ≥ 3×ULN and TBILI ≥ 2×ULN
- Concurrent (ALT or AST) ≥ 3×ULN and TBILI ≥ 2×ULN
- Concurrent (ALT or AST) ≥ 3×ULN and TBILI ≥ 2×ULN and ALP > 2×ULN
- Concurrent (ALT or AST) ≥ 3×ULN and TBILI ≥ 2×ULN and ALP ≤ 2×ULN or missing

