Concurrent measurements are those occurring on the same date.

Categories will be cumulative, i.e., a participant with an elevation of AST ≥ 10×ULN will also appear in the categories ≥ 5×ULN and ≥ 3×ULN.

A plot of peak ALT versus peak total bilirubin, both relative to the ULN will be provided. This eDISH plot (evaluation of drug-induced serious hepatotoxicity) will be divided into 4 quadrants by the lines through ALT ≥ 3×ULN and total bilirubin ≥ 2×ULN. The left lower quadrant is then considered normal or insignificant elevations in liver chemistries, the upper left quadrant indicates participants with possible Gilbert's cholestasis; the right upper quadrant are the possible Hy's Law participants; the right lower quadrant is possible Temple's Corollary (participants with ALT ≥ 3×ULN but not satisfying Hy's Law). Same plot will be provided for AST.

Liver function elevation may be repeated for China sub-population.

In addition, a listing of all total bilirubin, ALT, AST and ALP values for participants with a post-baseline total bilirubin ≥ 2×ULN, ALT ≥ 3×ULN or AST ≥ 3×ULN will be provided.

Urinalysis / urinalysis microscopic evaluation, hormonal tests, tuberculosis test, HIV test, serology

All test results for urinalysis /urinalysis microscopic evaluation, hormonal tests, serum and serology parameters will also be listed in dedicated listings:

- Urinalysis parameters:
 - Urinalysis full parameters: physical appearance, pH, specific gravity, protein, glucose, ketones, nitrite, leukocyte esterase, blood, urobilinogen, bilirubin, color
 - Urinalysis microscopic parameters: erythrocytes (RBC), leukocytes (WBC), epithelial cells, bacteria, crystals, casts

- Tuberculosis parameters: M. tuberculosis IFN Gamma Response by T-SPOT ELISPOT, Tuberculosis skin test (TST), M. tuberculosis IFN Gamma Response by QuantiFERON TB Gold ELISA
- Hormonal parameters: thyroxine free (Free T4), thyrotropin (Thyroid-Stimulating Hormone; TSH)
- HIV parameters: HIV test (HIV), HIV RNA viral load, CD4 Lymphocyte count (CD4LY)
- Serology parameters: hepatitis B virus (HBV), hepatitis C virus (HCV), hepatitis B DNA, hepatitis C RNA

Pregnancy test

Results for pregnancy and post-menopausal status as collected on the “Pregnancy Test” eCRF page will also be listed:

- Pregnancy parameters (serum or highly sensitive urine human chorionic gonadotropin (hCG))
- Post-menopausal status: FSH and estradiol parameters

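### SAP 15.3 sets its on-treatment liver categories and eDISH quadrants without a baseline condition, so participants with liver involvement who enter with raised values can be shown as possible Hy's Law with no change on treatment

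*SAP*

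**What the plan says.** SAP 15.3 (Liver function tests) gives the purpose: "ALT, AST and total bilirubin are used to assess possible drug induced liver toxicity". It then states: "The number and percentage of participants within each of the following liver function categories during on-treatment period will be described". The categories are ALT, AST, and either of the two, at ≥3, ≥5, ≥10 and ≥20×ULN; total bilirubin at ≥2×ULN; and same-date combinations such as "Concurrent (ALT or AST) ≥ 3×ULN and TBILI ≥ 2×ULN". That last combination is also split by ALP above 2×ULN versus not above or missing.

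For the eDISH display, "A plot of peak ALT versus peak total bilirubin, both relative to the ULN will be provided", with the same plot for AST. The dividing lines are at 3×ULN and 2×ULN, and "the right upper quadrant are the possible" Hy's Law participants. The lower right quadrant is labelled possible Temple's Corollary. No baseline exclusion, baseline stratum or liver-involvement subgroup is attached to the table or the plots.

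Protocol 5.1, criterion 7b, requires bilirubin ≤ULN and AST and ALT ≤1.5×ULN in general. It relaxes this as follows: "For participants with liver involvement in their tumor", AST and ALT may be up to 5.0×ULN and bilirubin up to 3.0×ULN.

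Baseline does appear elsewhere in SAP 15.3:
- shift tables, one parameter at a time, with the baseline of ALT, AST, ALP and bilirubin reduced to Normal or Abnormal (footnote c of Table 10);
- boxplots of change from baseline;
- a listing of every bilirubin, ALT, AST and ALP value for anyone who crosses 2×ULN (bilirubin) or 3×ULN (ALT or AST) after baseline.

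**The concern.** A table meant to screen for drug-induced injury should separate values that rose on treatment from values that were already raised. Here the entry criteria deliberately admit some participants whose liver tests may already lie above the reporting thresholds.

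The protocol expects such people. In Section 6.8 it makes a baseline-relative exception in its liver-test rule: "except for participants with liver metastases (for example) who begin treatment with Grade 2 AST or ALT". Table A2 of Appendix 5 places Grade 2 at AST or ALT above 3.0 and up to 5×ULN, which is the band in question. SAP 15.4 also shows that the plan can combine a threshold with a change: its blood pressure, pulse and respiratory-rate abnormalities each require both.

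What is at stake is how the liver safety summary is read. Immune-related hepatitis is an important identified risk (Protocol 2.3 and 6.9.2), and a row or quadrant that mixes entry status with on-treatment change can make the signal look larger than it is.

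**Working it through.** The plan states no figure on this point, so there is none to reproduce. The check is whether the entry limits and the reporting thresholds can be met together.

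**Inputs.** Entry limits from Protocol 5.1, criterion 7b; thresholds from SAP 15.3; planned size 135 from the Protocol 1.1 synopsis.

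**Step 1: overlap, in multiples of ULN.**

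| SAP 15.3 category | With liver involvement (AST/ALT ≤5.0, bilirubin ≤3.0) | All others (AST/ALT ≤1.5, bilirubin ≤1.0) |
|---|---|---|
| ALT or AST ≥3 | overlap 3.0–5.0 | none |
| ALT or AST ≥5 | exactly 5.0 only | none |
| ALT or AST ≥10, ≥20 | none | none |
| Bilirubin ≥2 | overlap 2.0–3.0 | none |
| Concurrent ALT or AST ≥3 and bilirubin ≥2 | AST/ALT 3.0–5.0 with bilirubin 2.0–3.0 | none |

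A grid in steps of 0.1, with AST set equal to ALT, agrees: 21 × 11 = 231 combinations are both eligible and inside the concurrent region with liver involvement, and 0 without. Criterion 7b sets no ALP limit, so either of the two ALP sub-rows can also be met.

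**Step 2: worked cases.**
- *Case A.* Liver involvement, ALT 4.0×ULN and bilirubin 2.5×ULN at baseline. Eligible, since 4.0 ≤ 5.0 and 2.5 ≤ 3.0. With the same values on treatment, 4.0 ≥ 3 and 2.5 ≥ 2 on the same date, so the participant is counted in the ALT ≥3×ULN, bilirubin ≥2×ULN and concurrent rows and plotted in the upper right quadrant. As written: 1 possible Hy's Law case. Counting only participants not already in the category at baseline: 0.
- *Case B.* Liver involvement, ALT 4.0×ULN with bilirubin within normal limits, unchanged. Counted in the ALT ≥3×ULN row and plotted as possible Temple's Corollary.

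The eDISH sentence gives no window for the peak values, so it does not expressly leave baseline out either.

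**Step 3: do the other planned outputs correct this?** The shift tables take one parameter at a time, so they cannot show a joint ALT and bilirubin baseline; with baseline shown as Normal or Abnormal, a baseline of 1.2×ULN and one of 4×ULN fall together. The boxplots are also single-parameter. The ALP split speaks to cholestasis, not to baseline. The listing shows each participant's baseline but does not change a count or a plotted label.

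**Step 4: size.** The documents do not give q, the share of participants entering inside the concurrent region. The values below are assumptions, for scale only. The expected number flagged with no change is 135q, and the chance of at least one is 1 − (1 − q)^135.

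| Assumed q | 135q | Chance of at least one |
|---|---|---|
| 0% | 0 | 0 |
| 0.5% | 0.7 | 0.492 |
| 1% | 1.4 | 0.743 |
| 2% | 2.7 | 0.935 |
| 3% | 4.1 | 0.984 |

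One participant is 1/135 = 0.74%.

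**The case against.** The strongest reply is that the information is already in the same section. The listing covers everyone who could be miscounted, the biochemistry listing flags baseline values and gives change from baseline, and combined cases should be few enough to read one by one. This stands as far as it goes. A reader might infer that a genuine new case would be hidden among unchanged ones; the documents do not support that, because the listing would show it. What remains is that the summary rows and the quadrants are not corrected by it.

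A second reply is that attribution is made elsewhere. Under Protocol Appendix 4, conditions present at the start that do not worsen are not adverse events, and investigators weigh the underlying disease when judging causality. SAP 15.2.3.2 applies an etiology or biopsy test before an event counts as immune-related. Also, the table rows are numeric and carry no causal label; only the quadrants are named, and only as possible. All of this is fair and keeps the point to descriptive output. It does not remove it, since the SAP itself introduces these outputs as the assessment of drug-induced liver toxicity.

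Third, SAP 6.1 cuts the analyses to those for an abbreviated report. It keeps clinical laboratory evaluations but does not name the liver categories or the eDISH plots, so whether they will be produced is not stated. SAP Appendix 2, which may say how abnormal baselines are graded, is not in the text available here. Whatever it says could affect the shift tables, but the liver rows use ULN multiples rather than grades.

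Two further inferences should be resisted. Section 6.8 concerns treatment discontinuation and its baseline-relative part covers AST and ALT only, so the SAP does not contradict it. Nor is the single-arm design the cause: each participant's own baseline shows entry status, and no control group is needed for that.

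**Conclusion.** The point holds in a limited form. For participants with liver involvement, and for no one else, the entry limits overlap the ALT/AST ≥3×ULN rows, the bilirubin ≥2×ULN row, the concurrent rows and the corresponding eDISH quadrants. Unchanged baseline values are then displayed as on-treatment findings, so the descriptive liver signal can be overstated.

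It should not be read as affecting the whole trial population or the higher categories: ≥5×ULN is touched only at exactly 5.0, and ≥10 and ≥20×ULN not at all. Nor should a number of false cases be quoted. The documents give neither the proportion with liver involvement nor the proportion entering with raised values, and the count could be zero. They also give no expected number of true cases to set it against. The only firm figure is 0.74% of 135 per affected participant. The primary endpoint and the other efficacy results are untouched. This is a worthwhile, low-cost improvement to a safety display.

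**What to change.** In SAP 15.3, split the ALT ≥3×ULN, AST ≥3×ULN, ALT-or-AST ≥3×ULN, bilirubin ≥2×ULN and concurrent rows into participants who did and did not already meet that threshold at baseline, using the baseline definition in SAP 9.2. On both eDISH plots, give a different symbol to participants with baseline ALT or AST ≥3×ULN or bilirubin ≥2×ULN. While that text is open, state that peak means the on-treatment peak, in line with the table.

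The cost is a few table rows, a plot legend entry and minor programming. Baseline ALT, AST and bilirubin are already collected, and no clinical rule or assessment schedule changes.
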